### 5.6.3. Length of Study Observation

The length of the observation period (days) will be calculated as:

- (Date of last study visit [up to End of Follow-up Clinic Visit] – date of first study drug dose) +1.

The observation duration will be summarized for each treatment group using the number of patients (n), mean, standard deviation, median, Q1, Q3, minimum, and maximum.

The number (%) of patients with observation periods will be presented by specific time periods. The time periods of interest are specified as:  $\geq 1$  day,  $\geq 29$  days,  $\geq 57$  days,  $\geq 85$  days,  $\geq 113$  days,  $\geq 141$  days,  $\geq 169$  days,  $\geq 197$  days,  $\geq 225$  days,  $\geq 253$  days, and  $\geq 449$  days

### 5.7. Protocol Deviations

All major and minor protocol deviations are collected and reviewed on an ongoing basis throughout the study as described in the Protocol Deviation Definitions Document (PDDD).

Protocol deviations will be summarized for patients incurring any major deviation by count and percentage, and patients incurring each type of major deviation by count and percentage for FAS.

A patient listing of all major and minor protocol deviations will be provided.

### 5.8. Analysis of Efficacy Data

As a result of the DMC recommendation resulting in treatment discontinuation for all patients, no hypothesis testing will be conducted. The analysis of efficacy data will be descriptive based on the FAS by treatment group.

#### 5.8.1. Analysis of Primary Efficacy Variable(s)

##### 5.8.1.1. Primary Efficacy Analysis

The primary efficacy endpoint in the study is:

- Change from baseline to week 16 in the average daily LBPI NRS Score

Primary efficacy data will be summarized by baseline and change from baseline to each scheduled assessment time with descriptive statistics based on the FAS by treatment group.

No sensitivity analyses will be performed for the primary efficacy variable.

#### 5.8.2. Analysis of Additional Efficacy Variable(s)

Analyses of continuous efficacy endpoints will use the same analysis method as the primary efficacy variable.

For analysis of categorical efficacy endpoints, e.g., proportions of patients with  $\geq 30\%$  reduction from baseline to week 16 in the daily average LBPI NRS score, the Cochran Mantel Hanszel approach stratified by the randomization strata will be used with missing data considered as non-response.

## **Rescue Medication**

The percentage of patients who use rescue medication between baseline and week 16 will be summarized by the treatment group using the FAS.

Number of days patients used rescue medication during the treatment period (Day 1 to Week 2, Week 2 to Week 4, Week 4 to Week 8, Week 8 to Week 12, Week 12 to Week 16) will be summarized descriptively by treatment group. Weekly average amount of rescue medication use will be summarized by treatment group.

## **5.9. Analysis of Safety Data**

The analysis of safety and tolerability will be performed on the SAF, as defined in Section 3.2.

The safety analysis will be based on the reported AEs and other safety information (clinical laboratory evaluations, vital signs, 12-lead ECG, Physical Examination, etc.).

Treatment-Emergent Potential Clinically Significant Values (PCSV) in laboratory variables, vital signs and ECG are defined in Appendix 11.2.

**Period of observation:** The observation period will be divided into three segments: pre-treatment, on-treatment and post-treatment.

- The pre-treatment period is defined as the time between when the patients give informed consent and the start of study drug.
- The on-treatment period is defined as the time from first dose of study drug up to 28 days after the last dose of study drug.
- The post-treatment period is defined as the time starting 29 days after last dose of study drug (after the on-treatment period) to up to 24 weeks post the last dose of study drug (up to week 36).

Day 1 is the first day of study drug, Day -1 is the day before Day 1, and there is no Day 0.

The time interval to detect any on-treatment event or abnormality is between the first dose of double-blind study drug injection and the end of treatment plus 28 days. Data collected outside this interval will be excluded from the on-treatment estimation of descriptive statistics and identification of abnormalities for laboratory evaluations, ECGs and vital signs. All post-baseline data during the interval will be used in the PCSV analysis including scheduled and unscheduled assessments.

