7. STUDY TREATMENTS

7.1. Investigational Treatment

Fasinumab drug product is supplied for this study in 1 mL single-use pre-filled syringes that deliver 0.5 mL of 6 mg/mL solution to provide a single 3 mg dose of study drug.

All patients will receive SC injections of fasinumab or fasinumab-matching placebo. Patients will be randomized to 2 treatment arms in a 1:1 ratio to receive either fasinumab 3 mg SC Q4W or fasinumab-matching placebo SC Q4W. All SC injections will be in the abdomen, thigh, or upper arm. Instructions for dose preparation and study drug administration are provided in the pharmacy manual.

Doses of study drug must be given within ± 7 days from the scheduled dose date. If the window is missed, the dose should not be administered. The next dose should be administered at the next scheduled dosing date.

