10.4.4.1. Adverse Events

Definitions

For safety variables, 3 observation periods are defined:

- The pretreatment period is defined as the time from signing the ICF to before the first dose of study drug.
- The on-treatment period is defined as the day from first dose of study drug to the day of the last dose of study drug (week 12) + 4 weeks.
- The follow up period is defined as the time from the end of the on-treatment period (week 16) to the week 36 visit.

Treatment-emergent adverse events are defined as those that are not present at baseline or represent the exacerbation of a pre-existing condition during the on-treatment period.

Analysis

All AEs reported in this study will be coded using the currently available version of the Medical Dictionary for Regulatory Activities (MedDRA[®]). Coding will be to lowest level terms. The verbatim text, the preferred term (PT), and the primary system organ class (SOC) will be listed. The focus of adverse event reporting in the clinical study report will be on TEAEs. Post treatment AEs and all AEs during the study will be summarized similarly as TEAEs.

Summaries of all TEAEs by treatment group will include:

- The number (n) and percentage (%) of patients with at least 1 TEAE by SOC and PT
- TEAEs by severity (according to the grading scale outlined in Section 9.5.1), presented by SOC and PT

- TEAEs by relationship to treatment (related, not related), presented by SOC and PT
- Treatment-emergent AESIs (defined with a PT or a pre-specified grouping)

Deaths and other SAEs will be listed and summarized by treatment group.

Treatment-emergent adverse events leading to permanent treatment discontinuation will be listed and summarized by treatment group.

In addition, AESIs will be reported according to the adjudicated diagnosis. Imaging data related to AA including change from baseline in joint space width will be summarized.

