### **5.9.6. Analysis of 12-Lead ECG**

ECG parameters (Ventricular Rate, PR Interval, QRS Interval, QT Interval, RR Interval, QTcF QTcB interval) will be summarized by baseline and change from baseline to each scheduled

assessment time. PCSV summary of ECG parameters will be provided for on-treatment period, follow-up period, and overall for the SAF.

ECG status (i.e. normal, abnormal) will be reported. Shift tables will be provided to present the post-baseline status according to the baseline status (normal or missing / abnormal) by treatment.

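### The on-treatment period ends exactly on the Week 16 target day, so the ±7-day windows decide whether end-of-treatment ECG, laboratory and vital-sign data count as on-treatment or follow-up

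*SAP*

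**What the plan says.** SAP 5.9 sets the periods. The on-treatment period runs "from first dose of study drug up to 28 days after the last dose of study drug". It continues: "The post-treatment period is defined as the time starting 29 days after last dose of study drug". Day 28 after the last dose is therefore still on-treatment and day 29 is not. For laboratory tests, ECGs and vital signs the consequence is explicit: "Data collected outside this interval will be excluded from the on-treatment estimation of descriptive statistics and identification of abnormalities".

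The same SAP section words the limit a second way, counting the 28 days from the end of treatment rather than from the last dose.

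Protocol 10.4.4.1 uses the same rule (last dose at Week 12, plus 4 weeks) and treats the limit as identical with Week 16. It defines follow-up as "the time from the end of the on-treatment period (week 16) to the week 36 visit".

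The schedule is looser. Protocol 7.1 says: "Doses of study drug must be given within ± 7 days from the scheduled dose date". In SAP Appendix 11.1 Table 2 the Week 12 dosing visit is Day 85 (±7) and the Week 16 end-of-treatment visit is Day 113 (±7).

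In that table the ECG appears at screening, at Week 16 and at the treatment-period early-termination visit, and nowhere in follow-up. SAP 5.9.6 nevertheless states: "PCSV summary of ECG parameters will be provided for on-treatment period, follow-up period, and overall for the SAF".

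**The concern.** The limit leaves no room for the visit it is meant to capture. A patient who receives all four doses and attends every visit in window can have the end-of-treatment assessment on either side of it, for reasons of appointment timing alone.

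For vital signs, haematology and chemistry this costs one late value, since earlier treatment-period visits also supply data. For ECG it removes the only scheduled on-treatment value. That value then becomes the content of the follow-up PCSV table. A reader of SAP 5.9.6 output would naturally take the two columns as ECG findings on drug and after drug. For patients who received the Week 12 dose they would be the same end-of-treatment recording, divided by visit-day chance.

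There are also two ambiguities that a programmer must resolve. First, the two wordings of the limit in SAP 5.9 can differ by four weeks. Second, SAP 6.4 assigns data to nominal visits (with a mapping window of Days 100 to 127 for Week 16), so a late but compliant visit is a Week 16 value in by-visit tables while SAP 5.9 excludes it from on-treatment statistics.

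**Working it through.** **Inputs**
- Last dose at Week 12: Day 85, ±7 (SAP Appendix 11.1 Table 2; protocol 7.1).
- Week 16 visit: Day 113, ±7 (same table).
- On-treatment limit: last dose + 28 days, inclusive (SAP 5.9).
- Spread of actual days within the windows: not given in either document, so it is assumed and varied below.

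**Step 1, the plan's own figure.** 85 + 28 = 113. The limit is exactly the Week 16 target day, as the protocol assumes.

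**Step 2, range for compliant patients.** Let d be the dose-day deviation and v the visit-day deviation, each from −7 to +7. Days from last dose to visit = (113 + v) − (85 + d) = 28 + v − d. The range is 14 to 42 days. With the dose on target (d = 0) it is 21 to 35 days.

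**Step 3, share past the limit.** A visit is late when v > d.

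| Assumption | Share later than day 28 |
|---|---|
| Dose on target, visit uniform | 7/15 = 46.7% |
| Both uniform and independent | (225 − 15)/2 = 105; 105/225 = 46.7% |
| Triangular, peak on target, dose on target | 28/64 = 43.8% |
| Triangular, both vary | 45.8% |
| 25% of visits exactly on day 28, rest symmetric | (1 − 0.25)/2 = 37.5% |
| 50% exactly on day 28, rest symmetric | 25% |
| 75% exactly on day 28, rest symmetric | 12.5% |

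Systematically early or late visits could give anything from 0% to 100%.

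**Step 4, what allowance would suffice.** With both days uniform, a limit of +35 days is missed when v − d > 7: 7 + 6 + 5 + 4 + 3 + 2 + 1 = 28 combinations, 28/225 = 12.4%. A limit of +42 days (28 + 7 + 7) is missed by none.

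**Step 5, adverse events.** Only onsets between day 29 and a late visit change class before that visit. With both days uniform, the gap totals 560 days over the 225 combinations: 560/105 = 5.3 days on average among late visits and 560/225 = 2.5 days over all. With the dose on target it is 28/7 = 4.0 and 28/15 = 1.9 days. The on-treatment period is about 113 days.

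**Step 6, patients whose dosing stopped early.** With a last dose on Day 1, 29 or 57 the limit is Day 29, 57 or 85. An ECG on Day 113 is then 112, 84 or 56 days after the last dose.

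**Step 7, the limit counted from the end of treatment.** The schedule labels Week 16 as end of treatment. Read that way, end of treatment plus 28 days is 113 + 28 = Day 141, against Day 113 when the 28 days are counted from the last dose.

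**The case against.** The strongest defence is that a fixed window of one dosing interval after the last dose is a legitimate pre-specified choice. It matches the protocol's 4 weeks and the 28 days added in the exposure formula (SAP 5.6.2), and a window tied to visits would vary between patients. For treatment-emergent adverse events this stands, and that window should stay. It is weaker for scheduled measurements. These exist only at the visit, so visit timing already decides their class; assigning them by scheduled visit removes that dependence.

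It is also fair that nothing disappears. By-visit tables follow the nominal visit, and the overall ECG column in SAP 5.9.6 keeps every tracing. That limits the harm, but the two misleading columns would still be produced beside it.

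Finally, 63 patients had been randomized when dosing stopped, and SAP 5.8 drops hypothesis testing. No formal conclusion turns on this boundary. Still, SAP 1.1 gives continued safety monitoring as the reason for keeping patients in the study, and in descriptive tables the period label carries the interpretation.

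Three stronger readings are tempting, and the documents do not support them:
- *That a large share of patients' new adverse events stop being treatment-emergent.* SAP 5.9.2 classifies events by when they developed or worsened. Only those starting after day 28 move, including any first found and dated at a late visit, and post-treatment events are summarised in the same way. The exclusion in SAP 5.9 does not name neurologic examinations or adjudicated arthropathy, which SAP 5.9.10 and 5.9.9 summarise without this limit.
- *That missing ECGs will be counted as normal.* SAP 6 leaves patients with missing data out of percentages unless otherwise specified.
- *That patients stopped early are misclassified.* An ECG 56 to 112 days after the last dose is properly off-treatment, and the 42-day cap proposed below would also exclude it.

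**Conclusion.** The point holds for laboratory, ECG and vital-sign summaries. That the limit coincides with the Week 16 target day, that compliant visits span 14 to 42 days after a Week 12 dose, and that no follow-up ECG is scheduled all follow from the documents without any assumption.

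The share of visits affected does rest on an assumption. A reader might take 46.7% as the expected loss, but it requires independent, uniform scatter. If sites book Week 16 from the actual Week 12 dose, many visits will fall on day 28 and 12.5% to 37.5% is the better range. Any of these shares applies only to patients who received a Week 12 dose, a number the documents do not give.

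The consequence is material for the split ECG PCSV table and modest elsewhere. The two wordings of the limit in SAP 5.9 need reconciling whatever the scatter.

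**What to change.** Three changes before database lock:

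1. In SAP 5.9, for laboratory, ECG and vital-sign summaries and PCSVs only, count as on-treatment the next scheduled four-weekly visit after the last dose (Week 16 for a Week 12 dose), or the treatment-period early-termination visit, if it is no more than 42 days after that dose. Keep the treatment-emergent adverse event window at last dose + 28 days, as in protocol 10.4.4.1.
2. In SAP 5.9, replace the wording that counts 28 days from the end of treatment with wording anchored to the last dose, so that the section has one limit.
3. In SAP 5.9.6, replace the on-treatment/follow-up ECG PCSV split with one Week 16/early-termination post-baseline summary among patients with a post-baseline ECG. List days since last dose so that ECGs from patients whose dosing stopped early can be identified.

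The cost is SAP wording and one derivation. The downside is that up to 14 extra days (42 − 28) of laboratory, ECG and vital-sign data count as on-treatment, so this window differs slightly from the adverse-event window. The SAP should say so.

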### **5.9.1. Safety Endpoints**

Raw incidence rates will be summarized by treatment group based on the SAF.

### **5.9.2. Adverse Events**

The verbatim text, the preferred term, and the primary SOC will be listed in patient listings. Summaries that include frequencies and proportions of patients reporting AEs will include the preferred terms and the SOCs.

- *Pre-Treatment Adverse Events* are defined as AEs that developed or worsened during the pre-treatment period.

- *Treatment-Emergent Adverse Events (TEAE)* are defined as those that are not present at baseline or represent the exacerbation of a pre-existing condition during the on-treatment period.
- *Post-Treatment Adverse Events* are defined as AEs that developed or worsened more than 28 days after the last dose of study drug.

The focus of adverse event reporting in the clinical study report will be on TEAEs. Post-treatment AEs and AEs during the study will be summarized similarly as TEAEs.

Summaries of TEAEs by treatment group will include:

- Overview of TEAEs, summarizing number of events, summarizing number and percentage of patients within the specified category
  - Total number of TEAEs
  - Total number of Serious TEAEs
  - Patients with any TEAEs
  - Patients with any Serious TEAEs
  - Patients with any TEAEs leading to death
  - Patients with any TEAEs leading to withdrawal from study
  - Patients with any TEAEs leading to permanent study treatment discontinuation
- All TEAEs by SOC and PT
- All TEAEs by SOC, PT, severity
- Study drug related TEAEs by SOC and PT
- TEAEs resulting in Permanent Study Drug Discontinuation by SOC and PT
- AESI by SOC and PT
- Serious TEAEs by SOC and PT

Listing to include:

- Listing of AEs leading to death
- Listing of TEAEs leading to permanent study treatment discontinuation
- Listing of TEAEs leading to withdrawal from study
- Listing of Patients with Serious TEAEs
- Listing of Patients with AESIs
- Listing of all Joint Replacements

Counts will be provided according to treatment group for each PT within each primary SOC. Percentages will be calculated based on the SAF in each treatment group.

Primary SOCs will be sorted by decreasing frequency in the fasinumab group. Within each primary SOC, PTs will be sorted by decreasing frequency in the fasinumab group. For tables presenting severity of events, the worst severity will be chosen for patients with multiple instances of the same event.

TEAEs with preferred terms  $\geq 5\%$  in any treatment group will be summarized in the report.

### **5.9.3. Adverse Events of Special Interest**

AESIs will be listed and summarized by treatment group based on the SAF.

Radiograph data related to AA including change from baseline in joint space width will be summarized by SAF over time.

Knee Society Score questionnaire or Harris Hip Score questionnaire results will be listed if applicable.

### **5.9.4. Clinical Laboratory Measurements**

Laboratory test results will be summarized by baseline and change from baseline to each scheduled assessment time with descriptive statistics based on the SAF by treatment group.

Shift tables based on baseline normal/abnormal and other tabular and graphical methods may be used to present the results for laboratory tests of interest.

Listings will be provided with flags indicating the out of laboratory range values.

A Treatment-Emergent Potential Clinically Significant abnormal value (PCSV) is a laboratory value that was normal at Screening and Baseline but became abnormal and met PCSV criteria after treatment with study drug. Definition of PCSV is listed in [Appendix 11.2](#). Treatment Emergent Potentially clinically significant values (PCSVs) will be summarized based on the SAF by treatment group. Additional exploratory analyses using alternative cut-points may be conducted.

For hs-CRP, plots of means and medians of the observed values and change from baseline over time will be presented by treatment group.

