 13. Use of extended-release or controlled-release opioids (eg, oxycontin), transdermal fentanyl or methadone within 3 months prior to the screening visit
 14. Use of opioids with a morphine equivalent dose of ≥ 30 mg per day for more than 4 days per week
 15. Use of systemic (ie, oral or intramuscular) corticosteroids or intra-articular corticosteroids in any joint within 30 days prior to the screening visit (topical, intranasal, and inhaled corticosteroids are permitted)
 16. Epidural steroid injections within 3 months prior to the screening visit
 17. Botox injections for LBP within 6 months prior to the screening visit
 18. History of cannabis use for the treatment of LBP within the past 6 months prior to the screening visit
 19. History of (within 5 years prior to the screening visit) or current alcoholism, alcohol abuse, substance abuse, or abuse of prescription pain medication
 20. Is scheduled for JR surgery during the study period
 21. Signs and symptoms of carpal tunnel syndrome within 6 months of screening

22. History or presence at the screening visit of autonomic neuropathy, diabetic neuropathy, or other peripheral neuropathy, including reflex sympathetic dystrophy
23. Evidence of autonomic neuropathy
24. History or diagnosis of chronic autonomic failure syndrome, including pure autonomic failure and multiple system atrophy (Shy-Drager syndrome)
25. Poorly controlled diabetes (defined as any single value of hemoglobin A1c [HbA1c] >9.0%) at the screening visit
26. Confirmed elevated screening alanine aminotransferase (ALT) or aspartate aminotransferase (AST) ≥ 2.5 x upper limit of normal (ULN)
27. Resting heart rate of <50 beats per minute (bpm) or >100 bpm (by vital sign assessment or as captured during electrocardiogram [ECG] assessment) at the screening or randomization visits
28. History or presence of second or third degree heart block, first degree heart block with abnormal complex of Q, R, and S waves on an electrocardiogram (QRS), or bifascicular block by ECG at the screening visit
29. History or presence of orthostatic hypotension, as defined in Section 8.2.3.8, at the screening, pre-randomization, or baseline visits
30. History of poorly controlled hypertension, as defined by:
 - a. Systolic blood pressure ≥ 180 mm Hg or diastolic blood pressure ≥ 110 mm Hg at the screening visit

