### 6.1. Definition of Baseline for Variables

Unless otherwise specified, the baseline assessment for all efficacy measurements/ patient reported outcomes will be the latest available valid measurement prior to or on the day of randomization. Baseline for safety assessments such as labs, ECGs, vital signs etc. will be the latest assessment prior to the start of treatment.

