eDiary compliance 			X		X	X	X	X									
Concomitant therapies	X	X	X	X	X	X	X	X	X	X	X	X	X	X	X	X	X
Safety:																	
Weight	X								X	X					X	X	
Vital signs	X	X	X		X	X	X	X	X	X	X				X	X	
Orthostatic blood pressure and heart rate assessment 	X	X	X		X	X	X	X	X	X	X				X	X	
Electrocardiogram	X								X	X							
Physical examination	X								X	X					X	X	
Neurologic examination	X Full		X Brief		X Brief	X Brief	X Brief	X Brief	X Full	X Full	X Brief				X Full	X Full	

	Screening/ Pre-rand		Treatment Period								Follow-up Period						
Study Week	Screen	Pre-rand	Base-line	Wk 1	Wk 2	Wk 4	Wk 8	Wk 12	EOT Wk 16	ET  / JR Pre-op	Wk 20	Wk 24	Wk 28	Wk 32	Wk 36	ET  / JR Pre-op	EOS Wk 64
Study Visit/Phone	Visit 1	Visit 2	Visit 3	Phone 1	Visit 4	Visit 5	Visit 6	Visit 7	Visit 8		Visit 9	Phone 2	Phone 3	Phone 4	Visit 10		Phone 5 
Study Day (visit window)	Up to 30 days	7 to 10 days	1	8 (±1)	15 (±3)	29 (±7)	57 (±7)	85 (±7)	113 (±7)		141 (±7)	169 (±7)	197 (±7)	225 (±7)	253 (±7)		449 (±7)
Survey of autonomic symptoms	X		X		X	X	X	X	X	X	X				X	X	
Joint pain questionnaire	X		X		X	X	X	X	X	X	X				X	X	
Event-triggered imaging 				X	X	X	X	X	X	X	X				X	X	
Adverse events	----->																
SC injection site evaluation			X			X	X	X									
Bilateral X-rays (knee, hip, shoulder)	X 								X 	X 					X 	X 	
MRI (any knee with K-L ≥3 and any hip with K-L ≥2 at screening) 	X																
Pre-op questionnaire (JR) 										X						X	
EOS phone contact 																	X
MRI affected joint(s) - AA patients only 																	X
Laboratory Testing:																	
Hematology 	X					X	X	X	X	X					X	X	
Blood chemistry 	X					X	X	X	X	X					X	X	
ESR	X																
HbA1c 	X																
Urinalysis and urine electrolytes 	X								X	X					X	X	
FSH and estradiol 	X																

	Screening/ Pre-rand		Treatment Period								Follow-up Period						
Study Week	Screen	Pre-rand	Base-line	Wk 1	Wk 2	Wk 4	Wk 8	Wk 12	EOT Wk 16	ET  /JR Pre-op	Wk 20	Wk 24	Wk 28	Wk 32	Wk 36	ET  /JR Pre-op	EOS Wk 64
Study Visit/Phone	Visit 1	Visit 2	Visit 3	Phone 1	Visit 4	Visit 5	Visit 6	Visit 7	Visit 8		Visit 9	Phone 2	Phone 3	Phone 4	Visit 10		Phone 5 

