**Table 4: Criteria for Treatment-Emergent Potentially Clinically Significant Values (PCSV)**

Parameter	Treatment Emergent PCSV	Comments
Clinical Chemistry		
ALT*	
>3 and <math>\leq</math> 5 ULN and baseline <math>\leq</math> 3 ULN*
 
>5 and <math>\leq</math> 10 ULN and baseline <math>\leq</math> 5 ULN
 
>10 and <math>\leq</math> 20 ULN and baseline <math>\leq</math> 10 ULN
 
>20 ULN and baseline <math>\leq</math> 20 ULN
	
Enzyme activity must be expressed in ULN, not in IU/L.
 
FDA DILI Guidance July 2009.
 
Each category is calculated independently.
 
* At least one level is required; multiple levels are optional for phase 2/3 studies. If it is desirable to get the distribution across the different PCSV levels, additional shift table on <math>\leq</math>3, >3 to <math>\leq</math>5, >5 to <math>\leq</math>10, >10 to <math>\leq</math>20, and >20 category for baseline vs. post baseline may be provided

AST*	
>3 and <math>\leq</math> 5 ULN and baseline <math>\leq</math> 3 ULN*
 
>5 and <math>\leq</math> 10 ULN and baseline <math>\leq</math> 5 ULN
 
>10 and <math>\leq</math> 20 ULN and baseline <math>\leq</math> 10 ULN
 
>20 ULN and baseline <math>\leq</math> 20 ULN
	
Enzyme activity must be expressed in ULN, not in IU/L.
 
FDA DILI Guidance July 2009.
 
Each category is calculated independently.
 
* At least one level is required; multiple levels are optional for phase 2/3 studies. If it is desirable to get the distribution across the different PCSV levels, additional shift table on <math>\leq</math>3, >3 to <math>\leq</math>5, >5 to <math>\leq</math>10, >10 to <math>\leq</math>20, and >20 category for baseline vs. post baseline may be provided

Alkaline Phosphatase	>1.5 ULN and baseline $\leq$ 1.5 ULN	
Enzyme activity must be expressed in ULN, not in IU/L.
 
FDA DILI Guidance July 2009.

Parameter	Treatment Emergent PCSV	Comments
Total Bilirubin*	>1.5 and ≤ 2 ULN and baseline ≤ 1.5 ULN* >2 ULN and baseline ≤ 2.0 ULN	Must be expressed in ULN, not in μmol/L or mg/L. Categories are cumulative.  FDA DILI Guidance July 2009.  * At least one level is required; multiple levels are optional for phase 2/3 studies. If it is desirable to get the distribution of significant level, additional shift table on ≤1.5, >1.5 to ≤2.0 and > 2.0 category for baseline vs. post baseline may be provided

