Conjugated Bilirubin	(Direct Bilirubin >35% Total Bilirubin and Total Bilirubin >1.5 ULN) and (Direct Bilirubin ≤35% Total Bilirubin or Total Bilirubin ≤1.5 ULN) at baseline	Conjugated bilirubin dosed on a case-by-case basis.
ALT/AST and Total Bilirubin	(ALT >3 ULN and TBILI>2 ULN) and baseline (ALT ≤3 ULN or TBILI ≤2 ULN)  (AST >3 ULN and TBILI>2 ULN) and baseline (AST ≤3 ULN or TBILI ≤2 ULN)  (ALT >3 ULN and TBILI>1.5 ULN) and baseline (ALT ≤3 ULN or TBILI ≤1.5 ULN)  (AST >3 ULN and TBILI>1.5 ULN) and baseline (AST ≤3 ULN or TBILI ≤1.5 ULN)	FDA DILI Guidance July 2009.
ALT/AST and Total Bilirubin and ALP	(ALT >3 ULN and TBILI>2 ULN and ALP < 2 ULN) and baseline (ALT ≤3 ULN or TBILI ≤2 ULN or ALP ≥2 ULN)  (AST>3 ULN and TBILI>2 ULN and ALP < 2 ULN) and baseline (AST ≤3 ULN or TBILI ≤2 ULN or ALP ≥2 ULN)	FDA DILI Guidance July 2009.

Parameter	Treatment Emergent PCSV	Comments
CPK*	>3 and $\leq$ 10 ULN and baseline $\leq$ 3ULN* >10 ULN and baseline $\leq$ 10ULN	FDA Feb 2005. Am J Cardiol April 2006. Categories are cumulative. * At least one level is required; multiple levels are optional for phase 2/3 studies. If it is desirable to get the distribution of significant level, additional shift table on $\leq$ 3, >3 to $\leq$ 10, and > 10 category for baseline vs. post baseline may be provided
Creatinine	$\geq$ 150 $\mu$ mol/L (Adults) and baseline < 150 $\mu$ mol/L $\geq$ 30% change from baseline and <100% change from baseline $\geq$ 100% change from baseline	Benichou C., 1994 3 independent criteria
Uric Acid		Harrison - Principles of internal Medicine 17 th Ed., 2008.
Hyperuricemia	>408 $\mu$ mol/L and $\leq$ 408 $\mu$ mol/L at baseline	Two independent criteria
Hypouricemia	<120 $\mu$ mol/L and $\geq$ 120 $\mu$ mol/L at baseline	
Blood Urea Nitrogen	$\geq$ 17 mmol/L and <17 mmol/L at baseline	Two independent criteria
Chloride		Two independent criteria
Hypochloremia	<80 mmol/L and baseline $\geq$ 80 mmol/L	
Hyperchloremia	>115 mmol/L and baseline $\leq$ 115 mmol/L	
Sodium		Two independent criteria
Hyponatremia	$\leq$ 129 mmol/L and baseline > 129 mmol/L	
Hypernatremia	$\geq$ 160 mmol/L and baseline <160 mmol/L	
Potassium		FDA Feb 2005.
Hypokalaemia	<3 mmol/L and baseline $\geq$ 3 mmol/L	Two independent criteria
Hyperkalaemia	$\geq$ 5.5 mmol/L and baseline <5.5 mmol/L	
Total Cholesterol	$\geq$ 7.74 mmol/L and < 7.74 mmol/L at baseline	Threshold for therapeutic intervention.

Parameter	Treatment Emergent PCSV	Comments

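### SAP 5.9.4 requires a normal baseline for a treatment-emergent laboratory PCSV, Table 4 does not, and no laboratory PCSV summary covers the period more than 28 days after treatment

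*SAP*

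**What the plan says.** **Definition.** SAP 5.9.4 describes a treatment-emergent laboratory PCSV as "a laboratory value that was normal at Screening and Baseline but became abnormal and met PCSV criteria after treatment with study drug", and its next sentence refers to Appendix 11.2. SAP 5.9 does the same: "Treatment-Emergent Potential Clinically Significant Values (PCSV) in laboratory variables, vital signs and ECG are defined in Appendix 11.2". Table 4 in that appendix attaches its own baseline condition to nearly every criterion. For total bilirubin one criterion is ">2 ULN and baseline ≤ 2.0 ULN"; for the combined liver criterion it is "ALT >3 ULN and TBILI>2 ULN) and baseline (ALT ≤3 ULN or TBILI ≤2 ULN".

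**Baseline.** SAP 6.1 sets a single value: "Baseline for safety assessments such as labs, ECGs, vital signs etc. will be the latest assessment prior to the start of treatment". In the schedule of events (SAP Table 2), haematology and chemistry are drawn at Screening, Weeks 4, 8, 12, 16 and 36, and at early termination. Nothing is drawn on Day 1.

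**Period.** SAP 5.9 sets an interval from first dose to the end of treatment plus 28 days and then states: "All post-baseline data during the interval will be used in the PCSV analysis including scheduled and unscheduled assessments". SAP 5.9.6 specifies ECG PCSV summaries for the on-treatment period, the follow-up period and overall. SAP 5.9.4 names no period for laboratory PCSVs.

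**Protocol.** Section 10.4.4.2 asks for the number and percentage of patients with a PCSV for each laboratory test at any time after randomization. SAP 1.2.4, which lists changes from the protocol's statistical section, mentions only the addition of hs-CRP.

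**The concern.** Two rules are given for the same flag, and the SAP does not say which governs. One requires a normal starting value; the other requires only that the starting value had not already crossed the cut-off. Two programmers could both follow the SAP and report different numbers of patients. If 5.9.4 is applied as an extra condition on top of Table 4, the count can only stay the same or fall, which is the wrong direction of error for a safety table.

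The second point is a summary that the protocol requests and the SAP does not specify. Dosing was stopped early, and patients were encouraged to stay in off-treatment follow-up so that safety could still be monitored (SAP 1.1). The Week 36 laboratory draw belongs to that follow-up, yet no laboratory PCSV count includes it.

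**Working it through.** No stated figure has to be reproduced here. The check compares the two rules and then the calendar.

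**1. Rows of Table 4.** Laboratory rows: 20 chemistry + 10 haematology + 1 urinalysis = 31.

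- Rows requiring a normal baseline: 0.
- Rows with at least one criterion requiring only that baseline had not passed the cut-off: 30.
- Row with no baseline condition: 1 (hs-CRP).
- Some individual criteria set no baseline level at all: the creatinine percentage changes and the haemoglobin decrease of at least 20 g/L.

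**2. Can an eligible patient fall between the rules?** Protocol exclusion 26 ("Confirmed elevated screening alanine aminotransferase (ALT) or aspartate aminotransferase (AST") applies from 2.5 x ULN upward, so a baseline above ULN but below 2.5 x ULN is admissible. For ALT in multiples of ULN:

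| Baseline | Post-baseline | Table 4 | 5.9.4 |
|---|---|---|---|
| 0.8 | 4 | counted | counted |
| 1.5 | 4 | counted | not counted |
| 2.0 | 6 | counted | not counted |
| 2.4 | 12 | counted | not counted |

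For the third row, 6 lies in the band above 5 and up to 10 x ULN, and the baseline of 2 satisfies that band's condition of at most 5 x ULN. It is not a normal value, so 5.9.4 rejects it.

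**3. Two pre-treatment values or one?** SAP 5.9.4 names Screening and Baseline, but only one haematology and chemistry draw is scheduled before dosing. Under SAP 6.1 that Screening draw is the baseline unless an unscheduled sample exists. The double condition therefore usually tests one value twice.

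**4. The interval.** Interval end = day of last dose + 28. Scheduled post-baseline haematology and chemistry draws fall on Days 29, 57, 85, 113 and 253.

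| Last dose (on schedule) | Interval ends | Draws inside, of 5 |
|---|---|---|
| Day 1 | Day 29 | 1 |
| Day 29 | Day 57 | 2 |
| Day 57 | Day 85 | 3 |
| Day 85 | Day 113 | 4 |

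**5. Could visit windows bring Week 36 inside?**

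- Earliest Week 36 draw: 253 − 7 = Day 246.
- Latest fourth dose: 85 + 7 = Day 92. The interval ends on 92 + 28 = Day 120, and 246 − 120 = 126 days short.
- If the end of treatment is instead read as the Week 16 visit at its latest, 113 + 7 = Day 120, the interval ends on 120 + 28 = Day 148, and 246 − 148 = 98 days short.

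Week 36 is outside on either reading.

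**The case against.** **Table 4 is only a reference.** Appendix 11.2 introduces it as such and leaves the actual criteria to be agreed before database lock. At least five rows have no listed test or no scheduled post-baseline sample: total cholesterol, triglycerides, conjugated bilirubin, HbA1c and hs-CRP. So 5.9.4 could be read as a study-specific condition placed on top of generic cut-offs. The row count is fairly challenged, but removing those five leaves 31 − 5 = 26 rows, still with none requiring a normal baseline. The same introduction says the criteria are to be settled as part of the SAP, which argues for stating one rule. The layered reading would also make many of Table 4's baseline clauses redundant.

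**Missing baselines.** SAP 6.3 groups a missing baseline with normal, so 5.9.4 is not quite as strict as it reads. That handles missing values; it does not reconcile the rules for an abnormal baseline that was measured.

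**The period is silence, not a prohibition.** SAP 5.9 excludes later data from the on-treatment estimates, and ECG still receives follow-up summaries. It is true that 5.9.4 does not forbid a later summary. It does not specify one either, and the protocol asks for it. The ECG comparison has limited force because no ECG is scheduled after Week 16.

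**Early termination.** Protocol 10.6 allows fewer parameters to be summarized if the study ends prematurely. That concerns which parameters are reported, not the period of a summary that the SAP retains. SAP 1.2.4 also omits much larger changes, such as the dropped primary model, so its silence is weak evidence of intent.

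**Materiality.** This objection largely stands. The tables are descriptive, and no safety endpoint in SAP 4.5.1 is defined by laboratory PCSVs. Week 36 values still appear in the change-from-baseline summaries and in listings with out-of-range flags.

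**Conclusion.** Both points hold. The treatment-emergent definition in 5.9.4 is wrong as written because it contradicts the table it cites. The laboratory PCSV count that the protocol requests, which would include Week 36, is not specified in the SAP.

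The effect is confined to descriptive summary tables; no hypothesis test, error rate or sample size is involved, and individual values are not lost. The number of patients affected among the 63 randomized cannot be computed from the documents and may be zero. The documents also do not say how many doses each patient received, so the split of draws inside and outside the interval is known only by dose count.

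The conclusion assumes that normal means within the laboratory's reference range. The statement that 5.9.4 can only keep or lower the count further assumes that it is applied in addition to the full Table 4 criterion and that missing baselines are treated alike under both rules. This should be corrected before database lock, but it is not a critical defect.

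**What to change.** 1. In SAP 5.9.4, replace the requirement of a normal value at Screening and Baseline with: *a post-baseline value meeting the Table 4 criterion, including its baseline condition where one is given*. This makes Table 4 the operative rule; the missing-baseline convention in 6.3 can stay.
2. Summarize laboratory PCSVs for the on-treatment period, the follow-up period and overall through Week 36, as 5.9.6 does for ECG.
3. If the 28-day limit is meant to be the only period, declare it in SAP 1.2.4 as a departure from Protocol 10.4.4.2.

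The same periods for vital signs would be consistent with ECG but are optional; the protocol does not ask for them.

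The cost is one SAP sentence and one or two table columns. PCSV counts may rise slightly, and follow-up values are harder to attribute to study drug, which is why they belong in a separate column.
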